2.0 RESEARCH OBJECTIVES

As noted earlier, this is a continuation study from the parent project showing that a cognitive-behavioral therapy (CBT) we designed to augment standard alcohol use disorder (AUD) treatment for patients with co-occurring anxiety disorder can improve the short-term (i.e., 4 month) alcohol outcomes of these patients compared to those receiving standard AUD treatment with a robust control group (relaxation training) in a randomized controlled trial. The CBT treatment in the parent study divided its focus equally between the goals of anxiety reduction (3 sessions) and decoupling anxiety and alcohol use/urges (3 sessions). However, because both the relaxation control group and the CBT group experienced roughly the same (not significantly different) degrees of anxiety reduction, we deduced that the added clinical benefit came from the decoupling focus of the CBT therapy, which was not present in the control group. This conclusion, along with the modest effect sizes obtained, motivated us to determine two additional pieces of information: 1) could increasing the de-coupling emphasis of the CBT beyond three sessions (i.e., increased dose) provide additional therapeutic benefits; and, 2) is the therapeutic value of the de-coupling elements only realized when combined with a purely anxiety reduction focus. The present study was design to answer these questions by dismantling the two both therapy foci into separate therapy groups (allowing for increased dose of each and an unambiguous evaluation of each foci on its own) and comparing these to the original CBT therapy that combined the therapy foci.

2.1 Primary Aim: To test the dismantled CBT effects by comparing the CBT-Decoupling (DC) group to the CBT-Anxiety Reduction (AR) group on alcohol outcomes. We predict that the CBT-DC group will have superior alcohol outcomes compared to the CBT-AR group. This result would confirm that the de-coupling therapy elements are more active in improving AUD outcomes than are the anxiety reduction therapy elements.

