2.2 Secondary Aim: To test dose vs. synergy effects of de-coupling therapy by comparing the CBT-DC group to the CBT-Original (O) group on alcohol outcomes. We predict that the CBT-DC group will have superior alcohol outcomes compared to the CBT-O group. This result would show the dose-response effects of de-coupling therapy on alcohol outcomes (6 vs. 3 DC sessions) and confirm that the de-coupling therapy effect on alcohol outcomes is not dependent upon its combination (synergy) with anxiety reduction elements. Alternatively, if CBT-O is superior to CBT-DC, then the critical role of synergy would be demonstrated.

2.3 Tertiary Aim: To test the dose effects of anxiety reduction therapy by comparing the CBT-AR group to the CBT-O group on alcohol outcomes. We predict that the CBT-O group will have superior alcohol outcomes compared to the CBT-AR group. Assuming synergy was ruled out in the Secondary Aim, this result would further confirm the hypothesized dose-response effects of de-coupling therapy on alcohol outcomes (3 vs. zero DC sessions). Alternatively, if the CBT-AR group is superior to the

CBT-O group, then a critical role for the higher dose of anxiety reduction therapy would be demonstrated.

2.4 Mechanism Manipulation Checks: Compare groups on pre- to post-treatment change in mechanism process measures. Determining that the interventions affected the targeted mechanism in the dose-dependent manner intended (e.g., reduction in AR-AOEs is greatest in the CBT-DC group) will allow group differences obtained to be attributed to the action of the targeted mechanisms.

2.5 Time-Dependent Effects: Explore time-dependent effects between mechanism process measures and alcohol outcomes from BL through 1-mo, 4-mo, and 8-mo FU assessments. These results will allow for causal inferences between mechanisms and outcomes by demonstrating temporal priority in change.

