Eliminating the anxiety disorder – so goes this line of thought – should eliminate its adverse effects on alcohol outcomes. Somewhat surprisingly, however, empirical tests of this idea have not been strongly supportive. Book and colleagues (2008, 2013), for example, found that while social anxiety disorder was well-treated by an SSRI in a group of hazardous drinkers who reported self-medication with alcohol, actual levels of pathological alcohol use remained virtually unchanged following treatment. Similarly, most studies find that adding a standard psychological (e.g., CBT) or pharmacological (e.g., SSRI) anxiety treatment to standard AUD treatment improves anxiety outcomes without improving alcohol outcomes (Bowen et al., 2000; Randall et al., 2001; Schadé et al., 2005). Pursuing this idea further, Hobbs et al. (2011) conducted a meta-analysis of all randomized controlled trials in which a standard CBT or pharmacological treatment for a co-occurring anxiety or depression disorder was given along with standard AUD treatment (study N=15). While there was a medium effect relative to control/placebo for anxiety outcomes ($d = .52$), there was only a small effect for alcohol outcomes ($d = .22$). While better internalizing disorder outcomes (i.e., above the median effect; $d = .32$) were associated with better alcohol outcomes, alcohol and anxiety outcomes were measured at the same time point; i.e., worse alcohol outcomes could have promoted worse anxiety outcomes rather than vice versa.

3.4. Interim summary. There is no affirmative evidence that treating a co-occurring anxiety disorder alone eliminates pathological alcohol use and there is some affirmative evidence that it does not. Treating co-occurring anxiety disorder in parallel with a standard AUD treatment typically provides moderate anxiety relief, but does little to improve AUD treatment outcomes; i.e., effects are sufficiently small to require pooling across multiple studies to identify small effects as significant.

3.5. Concepts aimed at promoting breakthroughs in the treatment of co-occurring disorders.

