4.3. Parent R01: Studies and Results

4.3.1. Recruitment. Over the four-year recruitment period for the RCT (Aim 2), we enrolled and randomized 344 cases. This works out to 86 randomized cases per year. In the final year of recruitment for the randomized study, we recruited 88 cases. In the no-cost extension period, we recruited 115 AUD TAU only cases. Based on this, we estimate we can typically recruit about 2 cases per week in the proposed work.

4.3.2. Retention. Over the life of the study, our retention rate was 78.5% (i.e., attrition was 21.5%) at the four-month follow-up. Our retention procedures improved significantly as indicated by an 87% retention rate in the final year (i.e., attrition about 13%). Based on this, we estimate a 75% retention rate in the proposed work.

[figure not shown]

4.3.2. Findings. As can be seen in the graphs, the alcohol outcomes obtained in the CBT group were superior to the other groups in all cases. The effects between the randomized groups (CBT vs. PMRT) were small for categorical outcomes (any drinking: $X^2 = 4.05$, $p = .04$, $d = .26$; and any three consecutive days drinking: $X^2 = 3.71$, $p = .05$, $d = .25$) and medium for count outcomes (drinks per month: $X^2 = 25.63$, $p < .001$, $d = .68$; drinking days per month ($X^2 = 10.23$, $p = .001$, $d = .42$; and number of binge days per month: $X^2 = 13.46$, $p < .001$, $d = .48$

[the latter is not shown in the graph]). These results support the key study hypothesis from Aim 2 of

the parent R01; i.e., that CBT would produce superior alcohol outcomes relative to a randomized active treatment control. They further demonstrate that the active treatment control, PMRT, did not significantly improve alcohol outcomes relative to TAU controls; however, since the TAU group was not randomized, caution must be taken when interpreting the latter findings. Although patient's "principal" anxiety disorder did not moderate these study results, level of BL anxiety was the only significant moderator; i.e., lower BL anxiety was associated with reduced CBT effects.

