competing interests in delivering therapeutic levels of the interventions for both theoretically central mechanisms (anxiety reduction and anxiety-alcohol de-coupling) while: 1) not interfering with the full day of standard AUD programming; 2) beginning at least one week after detoxification to accommodate recruitment time and to ensure therapy is delivered post-acute detoxification; and, 3) concluding treatment prior to discharge from the 28-day residential AUD program to avoid conflicts with re-location, return to place of employment, transportation etc. These parameters will apply to the renewal project conducted in the same institutional setting as the parent R01. The CBT-O group in the renewal work will be the same CBT protocol used in the parent R01; i.e., the three-session AR content set plus the three-session DC content set for a total of six sessions. The two dismantled CBT therapy conditions will include one of the three-session content sets (AR or DC) plus one additional session devoted to each of the three clinical domains (cognitive restructuring, coping skills, and exposure/habituation) within that set for a total of six sessions for all therapy groups.

6.5.2. Elements common to all three CBT therapy group conditions:

a) Psycho-Education in which the participant is introduced to the basics of the CBT model of therapy. This portion of the treatment is largely didactic and includes powerpoint slides that are narrated by the therapist.

b) Cognitive Coping Skills in which the participant is taught how to distinguish between thoughts, feelings and situations that are associated with negative affect (i.e., stress, anxiety and depression) and how each of these components interact with the others. Participants are then taught and practice a standard CBT skill referred to as "cognitive-restructuring" in which thoughts and beliefs that aggravate negative affect through their inaccuracy, incompleteness, or exaggeration are systematically examined and modified to better align with probabilistic reality and logical inference. This process has been shown in 100s of separate studies to improve anxiety and depression symptoms in psychiatric patients.

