The principal power estimate focuses on categorical analyses since these will provide the most conservative power estimates and because we have somewhat more information available to estimate these outcomes for the Primary Aim study groups. (ES for continuous/count alcohol outcomes all demonstrated larger group effects than the categorical outcomes in the parent R01 [Kushner et al. 2013-a].) The best estimate for the categorical CBT-AR alcohol outcome comes from the PMRT group (also devoted exclusively to anxiety reduction) in the parent R01 (i.e., 53% relapse at four months). The parent R01 does not provide a point estimate for the CBT-DC group relapse rate but our prediction that the CBT-DC group will ameliorate all (or most) of the deleterious effect on recovery conferred by a co-occurring anxiety disorder allows us to place this estimate at 21%; i.e., the relapse rate at four months of an AUD treatment group with no co-occurring anxiety disorder (Kushner et al., 2005; also see Driessen et al., 2001 for similar estimates). These estimated results would represent a large effect size ($OR = 4.2$), which would require a sample of only 41 per group to identify an effect at an $\alpha = .05$ level with 80% power; however, a larger sample size would be required to identify other predicted effects with the same power. Further, we cannot be certain that our empirically- and theoretically-informed prediction that the CBT-DC will mitigate all/most of the risk for relapse conferred by co-occurring anxiety disorder is correct until the study is conducted. Therefore, we also calculated a minimum detectable ES showing that we could detect an OR as small as 2.3 with 80% power in the planned sample size using a two-tailed test and 0.05 alpha-level. Although we would be at a higher risk of missing effects even smaller than this, such negative findings would not constitute a meaningful Type II error because they would be of increasingly trivial clinical importance (e.g., Ferguson, 2009). **Therefore, the Primary Aim will be put to a meaningful and scientifically valid test under a wide range of clinically meaningful effect sizes.**

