7.6. Secondary Aim: To compare the CBT-DC and CBT-O groups on alcohol outcomes

The importance of this comparison includes confirming our hypothesis that 6 DC sessions are superior to 3 DC sessions in terms of alcohol outcomes (DC dose: high vs. low) while also ruling out the alternative hypothesis that, contrary to study predictions, de-coupling therapy elements can only exert a therapeutic effect on alcohol outcomes when combined with anxiety reduction elements ("synergy"). Regarding the affirmative dose prediction, we can estimate the effect of the CBT-O group to be the same as that of the CBT in the parent R01 (i.e., 41% relapse at 4 months), while keeping all other parameters, including the CBT-DC group effect estimate of 21% relapse, the same as outlined for the Primary Aim. These estimated results would represent a medium effect ($OR = 2.6$), which would require a sample of 94 per group to identify with 80% power an effect with $\alpha = 0.05$. (Again, we anticipate continuous/count tests will have greater power than categorical tests.) If, however, contrary to our study predictions, synergy between the therapy components is necessary,

then we would expect CBT-DC to resemble TAU only in outcome (61% relapse) with the CBT-O result still being the same as in the parent R01 (again, 41% relapse). This would provide roughly the same power to detect the unexpected synergy effect as there will be to detect the predicted dose effect; albeit, with opposite directional effects.

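### CBT-O beating CBT-DC would be consistent with synergy but would not demonstrate it; the secondary-aim wording should be softened (minor)

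*Combined protocol and SAP*

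**What the plan says.** Section 2.0 gives two questions that the trial was designed to answer. The second is: "is the therapeutic value of the de-coupling elements only realized when combined with a purely anxiety reduction focus". The Secondary Aim, in the Study Aims and again in 2.2, assigns that question to CBT-DC against CBT-O. If CBT-DC wins, a dose effect is shown and dependence on the combination is excluded. For the reverse result the text reads: "Alternatively, if CBT-O is superior to CBT-DC, then the critical role of synergy would be demonstrated". No condition is attached.

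Section 7.6 puts rates on the reverse result. If the combination is necessary, "then we would expect CBT-DC to resemble TAU only in outcome (61% relapse", with CBT-O staying at 41%. It adds: "This would provide roughly the same power to detect the unexpected synergy effect as there will be to detect the predicted dose effect".

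Section 7.7 concedes that the tertiary contrast (CBT-O against CBT-AR) cannot separate dose from synergy. It presents the secondary contrast as free of that problem, because dose and synergy should point in opposite directions there. An AR effect is not mentioned in that comparison.

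**The concern.** Three explanations are possible for CBT-O doing better than CBT-DC, and the plan lists only one. Besides synergy, the three AR sessions may help drinking in their own right, and DC sessions 4 to 6 may add little. The last two together produce the result with no interaction.

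The plan keeps both open. Section 3.10 says a larger anxiety reduction might have affected alcohol outcomes, and the Tertiary Aim plans for an AR dose effect. Section 6.5.1 builds the dismantled arms from the three-session set "plus one additional session devoted to each of the three clinical domains", so DC sessions 4 to 6 return to domains already covered. A plateau is therefore plausible, although no section reports one.

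At stake is the interpretation of an unpredicted secondary result. An additive AR benefit combined with diminishing DC returns could be reported as proof that the components must be combined.

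**Working it through.** **Inputs.**
- CBT-AR 53%: section 7.5, where "The best estimate for the categorical CBT-AR alcohol outcome comes from the PMRT group".
- CBT-O 41%, TAU 61%, predicted CBT-DC 21%: section 7.6.
- 100 per group: section 7.8.
- Two-sided 0.05: section 7.5.
- Six sessions in every arm: section 6.5.1.

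**The plan's own figure.** For 41% against 21%, the odds ratio is (0.41/0.59)/(0.21/0.79) = 2.61. The continuity-corrected two-proportion formula gives 93 per group, against 94 stated (83 without correction). The figure is reproduced. For the synergy direction, 61% against 41%, approximate power at 100 per group is 81%, against 87% for the dose direction. Calling these roughly the same is fair. Both are powers for a difference between two arms, not for an interaction.

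**When CBT-O wins without interaction.** Write AR(k) and DC(k) for the benefit of k sessions.
- Benefit of CBT-O = AR(3) + DC(3).
- Benefit of CBT-DC = DC(6).
- CBT-O is better exactly when AR(3) > DC(6) − DC(3).

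If AR adds nothing and DC sessions 4 to 6 do no harm, CBT-O cannot be truly better and there is no false signal beyond ordinary type I error.

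**At the plan's rates, on the risk-difference scale.**
- Six AR sessions: 61 − 53 = 8 points. Three are worth 4 (AR linear) or 8 (AR complete by session three).
- CBT-O: 61 − 41 = 20 points. Three DC sessions are worth 20 − 4 = 16 or 20 − 8 = 12.
- Break-even: DC sessions 4 to 6 must be worth less than 4/16 = 25%, or 8/12 = 67%, of sessions 1 to 3.
- DC linear: CBT-DC = 61 − 32 = 29%, or 61 − 24 = 37%.
- Full DC plateau: CBT-DC = 61 − 16 = 45%, or 61 − 12 = 49%.

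**Chance that CBT-O is significantly better than CBT-DC.** Exact binomial enumeration, pooled two-proportion z-test. Every row has zero interaction; the dose shapes are assumptions.

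| Scenario | AR / O / DC relapse % | Chance |
|---|---|---|
| Plan's predicted order | 53 / 41 / 21 | about 0% |
| DC linear, AR linear | 53 / 41 / 29 | under 0.1% |
| DC linear, AR complete by session three | 53 / 41 / 37 | 0.6% |
| DC plateau, AR linear | 53 / 41 / 45 | 8.7% |
| DC plateau, AR complete by session three | 53 / 41 / 49 | 21.7% |
| AR strongly active, both linear | 29 / 41 / 53 | 42% |
| AR carries everything, linear | 21 / 41 / 61 | 83% |

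The last row gives the same CBT-O and CBT-DC rates that 7.6 assigns to synergy, so this contrast alone cannot tell the two apart. In the last two rows the primary contrast shows CBT-AR significantly better than CBT-DC in 94% and 100% of trials.

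**Sensitivity.** With TAU at 60% (section 4.4), the plateau figures become 8% and 18%. Section 3.3 reports that "there was only a small effect for alcohol outcomes" (d = .22). The logistic conversion gives exp(0.22 × π/√3) = 1.49 as an odds ratio, which takes 61% to 51%. The plateau rates for CBT-DC are then 46% and 51%, and the chances 11% and 31%.

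**The case against.** The strongest reply is that a realistic false signal needs two things together: a real AR effect on drinking, and sharply diminishing DC returns. Support for the first is thin. The 8-point gap sets relaxation training, used as a proxy for CBT-AR, against a cohort that was not randomized, and section 4.3 reports that "the active treatment control, PMRT, did not significantly improve alcohol outcomes relative to TAU controls". The d = .22 pools psychological and drug treatments for anxiety or depression. The second is assumed. The plan also predicts the opposite result, and every contrast needed for a joint reading is already planned. All of this stands, and it makes the point minor. It does not rescue the word used in 2.2: no section makes the synergy reading depend on the other contrasts. The mechanism checks in 7.8 compare process measures, so they would look alike under synergy and under a plain AR effect. They would reveal a plateau only if it showed in those measures.

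A reader might go further and infer that a false synergy claim is likely, pointing to the 42% and 83% rows. Those rows need CBT-AR at 29% or 21%, far from the planned 53%, and the trial's headline comparison would then contradict a synergy claim.

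A reader might also infer that synergy should be denied whenever CBT-O fails to beat CBT-AR. That contrast has only about 42% power at 53% against 41%, so failure is the likelier result even if the plan's rates are right. If synergy is real (CBT-DC 61%, CBT-O 41%) and CBT-AR is at 53%, requiring CBT-O to beat both arms cuts detection from 83% to 39%. It lowers the plateau false positives only from 8.7% to 6.8% and from 21.7% to 15.0%.

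**Conclusion.** The inference rule is wrong as written, and the point is minor. CBT-O superior to CBT-DC is compatible with synergy, but also with an independent AR benefit that exceeds what DC sessions 4 to 6 add. At the plan's rates the chance of a false synergy conclusion is under 1% with linear DC and about 9% to 22% at a full DC plateau. These figures assume additive effects on the risk-difference scale, 100 analysed per group, and a TAU rate from a non-randomized cohort. The algebraic condition does not depend on those rates.

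The documents do not support extending this to the primary aim. The primary analysis, the tests, alpha and the sample size are untouched.

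**What to change.** - **Study Aims and 2.2:** replace the claim that synergy would be demonstrated with a statement that the result would be consistent with synergy.
- **Study Aims, 2.2 and 7.6:** name an independent AR benefit and diminishing DC returns as alternatives. Say that the result will be read alongside the estimates and confidence intervals for CBT-DC against CBT-AR and CBT-O against CBT-AR.
- **Reading rules:** if CBT-AR is superior to CBT-O or to CBT-DC, state that AR content may explain the result. Do not treat a non-significant CBT-O against CBT-AR result as evidence against synergy. Note that CBT-O superior to both arms supports synergy without proving it, because additive components with diminishing returns give the same pattern.
- **7.6:** describe the roughly 80% power as power for the CBT-O against CBT-DC difference.
- **7.7:** add an AR effect to the parenthesis that sets dose against synergy.

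No test, alpha or sample size changes. The cost is a more cautious claim if synergy is real.

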f) Between session practice and monitoring will be assigned following each of the six CBT therapy sessions that will focus on practicing the skill taught in the session and keeping a simple record of their anxiety level and urge to use alcohol between the sessions as well as whether they were able to effectively use the therapy skill to reduce the negative affect/urge.

6.5.2. Elements distinguishing the three randomized CBT therapy group conditions:

a) CBT-Anxiety Reduction Condition: Those assigned to this group will undergo all of the CBT elements outlined above but with all six sessions focused on negative affect without specific reference to alcohol alcohol use.

b) CBT Anxiety-Alcohol Interaction Condition: Those assigned to this group will undergo all of the CBT elements outlined above but with all six sessions focused on the interaction of negative affect with alcohol use/urges.

c) CBT Combination Condition: Those assigned to this group will undergo all of the CBT elements outlined above but with three of the six sessions focused exclusively on reducing negative affect without reference to alcohol use and the other three sessions focused exclusively on the interaction of negative affect with alcohol use/urges.

6.5.3. Therapist training. The study PI is primarily responsible for training and supervision of study therapists. The training sequence established in the parent R01 will also be used in the renewal work including: 1) reading the therapist and patient treatment manuals; 2) observing training tapes that have been prepared for that purpose; 3) observing the trainer administer the treatment; and 4) being observed and critiqued by the trainer while delivering the treatment. Our experience suggests that delivery of the therapy via the structured PowerPoint slideshow (above) ensures a uniform delivery of the basic content of the therapy, even with newly trained therapists. Supervision with the PI takes place on a weekly basis throughout the treatment phase of the project (separately for each therapist) in which the progress of each case is discussed and any treatment issues are resolved.

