7.7. Tertiary Aim: To compare the CBT-O and CBT-AR groups on alcohol outcomes

The importance of this comparison includes confirming our hypothesis that 3 DC sessions are superior to zero DC sessions (DC dose: low vs. none) in terms of alcohol outcomes, while also exploring the alternative hypothesis that, contrary to study predictions, a high vs. a low dose of anxiety reduction therapy (i.e., 6 vs. 3 sessions) is needed to improve alcohol outcomes. Regarding the former, just as the CBT-DC group has three more DC sessions than the CBT-O group (6 vs. 3), the CBT-O group has three more DC sessions than the CBT-AR group (3 vs. zero). Regarding the affirmative dose prediction, we anticipate that the size of this effect will be the same as the size of the effect for the Secondary Aim: i.e., requiring 94 cases per group to obtain 80% power to detect an effect with alpha set at the .05 level. However, this dose-based prediction, if confirmed, will be somewhat more ambiguous than in the Secondary Aim because it could result either from the greater DC dose (as predicted) or DS-AR synergy. (In the Secondary Aim, by contrast, the group effects for dose and synergy should be in the opposite direction.) Alternatively, if the CBT-AR group is superior to the CBT-O group, this would suggest unambiguously that a higher dose of anxiety reduction is more important to improving alcohol outcomes than is a lower dose, even when combined with a low dose of de-coupling therapy.

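### The Tertiary Aim contrast swaps three de-coupling sessions for three anxiety-reduction sessions, so CBT-AR superiority shows an anxiety-reduction dose effect only under an assumption the plan does not state

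*Combined protocol and SAP*

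**What the plan says.** Section 2.3, repeated under Study Aims at the front of the protocol, gives the Tertiary Aim as "To test the dose effects of anxiety reduction therapy by comparing the CBT-AR group to the CBT-O group on alcohol outcomes". The prediction is that CBT-O will do better. For the opposite result, CBT-AR better than CBT-O, both places conclude: "then a critical role for the higher dose of anxiety reduction therapy would be demonstrated". Section 7.7 is firmer: "this would suggest unambiguously that a higher dose of anxiety reduction is more important to improving alcohol outcomes than is a lower dose". That sentence ends by noting that the lower AR dose would have been given together with some de-coupling therapy.

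The arms are described in Section 6.5. CBT-AR is delivered "with all six sessions focused on negative affect without specific reference to alcohol alcohol use". CBT-O is "the three-session AR content set plus the three-session DC content set for a total of six sessions". Section 6.5.1 builds each dismantled arm from one three-session content set plus one extra session for each clinical domain "within that set for a total of six sessions for all therapy groups".

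Section 7.7 gives both differences between the two arms. On the AR side it contrasts "a high vs. a low dose of anxiety reduction therapy (i.e., 6 vs. 3 sessions"; on the DC side it notes that "the CBT-O group has three more DC sessions than the CBT-AR group (3 vs. zero". If CBT-O wins, Section 7.7 accepts that either DC dose or synergy could be the cause. It attaches no such caution to a CBT-AR win.

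**The concern.** A test of the dose of one component needs the other component held fixed. Here the AR count falls from six to three while the DC count rises from zero to three, and no other pair of arms varies AR with DC constant. The plan treats this contrast as confounded when CBT-O wins and as clean when CBT-AR wins, but the confounding is the same in both directions.

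Section 3.10 gives, as one reason not to drop AR, the possibility that a larger anxiety reduction would have affected alcohol outcomes. The Tertiary Aim is the only aim labelled as testing AR dose. If CBT-AR won, the report would already have wording that credits the AR dose, and the choice of which component to expand could rest on an attribution the comparison cannot make alone.

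**Working it through.** **The plan's own figure.** Section 7.7 carries over 94 per group from Section 7.6 (41% vs 21%, 80% power, alpha 0.05). With d = 0.20 and mean rate 0.31, the usual two-sided formula gives n = [1.96·√(2·0.31·0.69) + 0.842·√(0.41·0.59 + 0.21·0.79)]² / 0.20² ≈ 83. With the continuity correction, (n/4)·[1 + √(1 + 4/(n·d))]², it gives 93, within one of the stated 94. Whether that is the right effect size for this contrast is a separate question. Nothing below depends on it.

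**Inputs (Sections 6.5.1, 6.5.2 and 7.7).**

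| Arm | AR sessions | DC sessions | Total |
|---|---|---|---|
| CBT-AR | 6 | 0 | 6 |
| CBT-DC | 0 | 6 | 6 |
| CBT-O | 3 | 3 | 6 |

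**Step 1: what the contrast estimates.** Let r(a,d) be the relapse rate with a AR and d DC sessions. Then

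r(6,0) − r(3,3) = [r(6,0) − r(3,0)] + [r(3,0) − r(3,3)].

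The first bracket is the AR dose effect. The second is the effect of three DC sessions added to three AR sessions, including any effect of combining them. No arm supplies r(3,0), so the brackets cannot be separated.

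**Step 2: does the third arm help?** In every arm AR + DC = 6, so the correlation of the two counts is −1.0. The matrix with columns (1, AR, DC) has rows (1,6,0), (1,0,6), (1,3,3) and rank 2 of 3. Adding an AR×DC column (0, 0, 9) gives rank 3 of 4. Let bAR and bDC be benefit per session and g the synergy coefficient, with benefit linear in sessions. Then

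- CBT-AR − CBT-DC = 6bAR − 6bDC
- CBT-AR − CBT-O = 3bAR − 3bDC − 9g
- CBT-O − average of the other two = (3bAR + 3bDC + 9g) − (3bAR + 3bDC) = 9g

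Even with linearity assumed, the data give bAR − bDC and g, but never bAR alone.

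**Step 3: one result, several explanations.** A CBT-AR advantage of 0.3 (arbitrary benefit units) arises from each of these:

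| bAR | bDC | g | 3bAR − 3bDC − 9g |
|---|---|---|---|
| 0.1 | 0 | 0 | 0.3 |
| 0 | −0.1 | 0 | 0.3 |
| 0.05 | −0.05 | 0 | 0.3 |
| 0.1 | 0.1 | −0.0333 | 0.3 |

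The second row has no AR effect at all. In the fourth, the AR and DC benefits cancel and the advantage comes wholly from antagonism.

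**Step 4: when the plan's conclusion does follow.** Suppose adding three DC sessions to three AR sessions does not raise relapse, so r(3,3) ≤ r(3,0). If CBT-AR wins, r(6,0) < r(3,3) ≤ r(3,0), and the AR dose effect is real. This needs no linearity. It is the missing assumption.

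**Step 5: the other results.** With bAR = bDC = 0.1 and g = 0, the contrast is 0.3 − 0.3 = 0 although AR dose matters. If DC sessions help more than extra AR sessions, CBT-O wins although AR dose still matters.

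**The case against.** The strongest reply is that the plan is more careful than its short statements suggest.

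- **Disclosure.** Section 7.7 states the DC difference itself, and its full sentence mentions the DC content that accompanies the lower AR dose. Read generously, it says that six AR sessions beat three plus three, which is the net effect. This stands against any suggestion that the difference is hidden. But the sentence still credits AR dose and claims no ambiguity, and Section 2.3 and Study Aims lack even that clause.
- **Mechanism checks.** Sections 2.4 and 7.8 make attribution to a mechanism depend on showing the expected change in process measures by arm. So the plan does not commit to the AR-dose reading regardless of other evidence. The checks may support attribution, but they do not remove the collinearity for alcohol outcomes.
- **DC harm is implausible.** The documents give no evidence that DC sessions are harmful or work against AR. The synergy scenario in Section 7.6 puts CBT-DC level with treatment as usual, not below it. The parent trial had 41% relapse with the combined CBT against 53% with relaxation, which Section 7.5 takes as the best proxy for CBT-AR. This makes the assumption reasonable. It does not make it stated or tested: the parent trial's comparator was relaxation training, not an AR-only form of the CBT.

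Two stronger readings are tempting. A reader might infer that the plan would count a null result, or a CBT-O win, as evidence against an AR dose effect. It says no such thing. From a CBT-O win, Section 2.3 infers only a DC dose-response, and only once synergy is ruled out; Section 7.7 calls that result somewhat ambiguous; no section interprets a null. A reader might also try to size the error from the plan's relapse rates. That requires a rate for three AR and no DC sessions. The documents have none, and the 53% in Section 7.5 is their estimate for CBT-AR itself.

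**Conclusion.** The point holds as one of inference and wording. CBT-AR against CBT-O estimates the net effect of exchanging three DC sessions for three AR sessions, and is mislabelled as a test of AR dose. The AR-dose conclusion from a CBT-AR win is not false. It is conditional on DC content, alone or combined with AR, not being detrimental, and the plan claims it without that condition.

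The finding of non-identifiability rests only on the session counts in Section 6.5; the size of the possible misattribution cannot be derived from the documents, and the 0.3-unit examples are illustrations. The overstatement affects a tertiary aim, in the direction the sponsor does not predict. It does not touch the Primary Aim or the direct comparison of the two packages as delivered.

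**What to change.** Edit three places: Study Aims, Section 2.3 and Section 7.7.

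1. Restate the Tertiary Aim as *the net effect on alcohol outcomes of six AR and no DC sessions compared with three AR and three DC sessions*.
2. In Study Aims and Section 2.3, remove the statement that a critical role would be demonstrated. In Section 7.7, remove *unambiguously*.
3. Put in their place: *If CBT-AR is superior to CBT-O, the result favours the AR-only package over the mixed package. It supports an AR dose effect only if DC content, or its combination with AR, is assumed not to be detrimental; because all arms total six sessions, the design cannot verify this. Mechanism checks will be reported as supporting evidence.*
4. As a precaution, since the plan does not claim otherwise, add: *A null result, or superiority of CBT-O, would not by itself rule out an AR dose effect.*

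Arms, tests and sample size are unchanged, and no new data or analyses are needed. The cost is a weaker tertiary conclusion.
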